correlated to TZD response will be defined as candidate genes and will be pursued using state-of-the-art molecular genetic approaches to define all common sequence variation and haplotype structure of the gene. We will then genotype these SNPs in our subjects to determine if these SNPs or haplotypes associate with TZD response. Although the 75 subjects we plan to recruit for this study will provide very rich phenotype and microarray information for defining TZD response and for selecting candidate genes to study, they will not be particularly powerful to discern the effect of specific gene variants on clinical response to TZDs.

However, they may be useful in discerning associations of gene variants with mRNA levels encoded by that gene (or within the same regulatory pathway). Thus, in the next stage of our study, we will take advantage of established collaborations with investigators of large prospective studies which involved a TZD intervention and for which relevant response traits have been collected, the DPP Study, and the TRIPOD Study (now continued as PIPOD).

[figure not shown]

Fig. 9. Timeline of the study

High throughput genotyping of 1536 SNPs in 100 candidate genes will be performed in these cohorts and association of SNPs and haplotypes with TZD response will be examined. It is our hope that in a subset of these 100 candidate genes we will find consistent evidence for a role in TZD response, e.g., altered mRNA levels in those with the variant SNP/haplotype and association with TZD response in both populations.

2. **Specific Aim 1. Defining interindividual variability in TZD response**

a. *Subject recruitment and screening*

Seventy-five subjects will be recruited for this study from the following sources:

- A large database belonging to the Division comprising over 500 subjects recruited at health fairs. These subjects have provided basic health information, given blood for genotyping, and indicated that we may contact them to inform them about future genetic studies. Additionally, some subjects have had oral glucose tests. We have previously successfully recruited subjects from this collection. This collection will also allow rapid identification of potential volunteers for our study if the focus should later change to a particular genotype or clinical profile.

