We will define the response variable for each of the 75 individuals studied to be the relative change in the primary (insulin sensitivity) and secondary (lipid, body fat composition, inflammatory markers, etc.) endpoints, expressed as the (post-intervention value minus the pre-intervention value) divided by the pre-intervention value. We will then begin with a series of descriptive analyses to identify the correlates of response to TZD therapy.

Specific Aim 1a. We will use conventional regression analysis and analysis of variance approaches to determine if baseline subject characteristics, including age, gender, ethnicity, and body mass index, are correlated with response. We will perform separate analyses for the primary and each of the secondary response variables. All analyses will also be adjusted for the baseline (pre-TZD treatment) value.

Specific Aim 1b. After identifying baseline variables that are significantly associated with response, we will then evaluate, as Specific Aim 1b, the pairwise relationships between the insulin sensitivity response and each of the secondary response variables. We predict that the insulin sensitivity responses will be correlated with the secondary trait responses, although the degree of correlation will not necessarily be equal in magnitude across all pairs (e.g., the correlation between the insulin sensitivity response and HDL cholesterol response may be greater than the correlation between the insulin sensitivity response and SBP response). We will estimate these correlations while adjusting for the effects of baseline variables identified in Specific Aim 1.

These correlation analyses will provide important descriptive information on this novel phenotype. For example, we predict that response in the secondary traits will generally be driven by the

insulin sensitivity response. Hence, we would expect there to be very limited little mean change in the secondary responses among those with limited insulin sensitivity response. Our proposed sample of 75 subjects should provide us with 80% power to detect correlations of size (population r) = 0.31.

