Statistical approach. To study the gene expression profiles that are related to the 3-month rosiglitazone intervention, we will compare the expression profile of the muscle (and fat) tissues from pretreatment subjects to that from post-treatment subjects. We will calculate and normalize gene expression levels by the Robust Multichip Average method (RMA) (37) and quantile normalization (11). The statistical significance of these comparisons will be assessed using LIMMA package software (27) (a linear model approach implemented in Bioconductor) or non-parametric methods (e.g., Kruskal-Wallis- or Mann-Whitney U-tests), using SAS software. A critical issue in microarray analysis is to avoid a high "false discovery rate" (9) (FDR; the probability that a gene is incorrectly identified as differentially expressed), due to the large number of genes compared. We will consider genes to be differentially expressed only if they meet criterion values for fold-change and p-value (for example, >1.5 and <0.05, respectively). For each analysis of differential expression, we will experiment with different combinations of criterion values and calculate the resultant FDR (using MULTTEST package in Bioconductor (61)) for each set of criteria, until we obtain acceptable stringency for fold-change, statistical significance and FDR (we anticipate using conservative FDRs in the range of 1-5%).

To study the association between these differentially expressed (DE) genes and the response of the primary and secondary traits to TZDs, for each DE gene, we will generate linear regression models using the change in the response of the primary (i.e., insulin sensitivity) and secondary responses to TZDs as dependent variables and the gene expression change in response of the treatment and demographic and clinical measures as the independent variables. For the regression models, we will report the adjusted squared correlation coefficient (R^2_{adj}), which corrects for the degrees of freedom. The association between each DE gene and each trait in response to TZDs can be measured by the adjusted squared correlation coefficient. The overall association with primary and secondary traits can be based on the score that is calculated as the weighted sum of the corresponding the adjusted squared correlation coefficients. The weights can be determined by principal component analysis. The importance of each gene can be determined by its score.

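### The gene-trait association is measured by the fit of the whole covariate model, so its value is not the gene's own contribution and is not comparable between traits

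*Combined protocol and SAP*

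**What the plan says.** The text is in the combined protocol and SAP, Section D.2.f (Laboratory methods), under Statistical approach.

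- **Model.** Each trait response is the dependent variable, with "the gene expression change in response of the treatment and demographic and clinical measures as the independent variables".
- **Statistic reported.** "For the regression models, we will report the adjusted squared correlation coefficient", described as correcting for degrees of freedom.
- **Interpretation.** "The association between each DE gene and each trait in response to TZDs can be measured by the adjusted squared correlation coefficient".
- **Score across traits.** It is "calculated as the weighted sum of the corresponding the adjusted squared correlation coefficients". On the weights: "The weights can be determined by principal component analysis". The matrix to be decomposed, the centring and the component are not given.
- **Use.** "The importance of each gene can be determined by its score".

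The paragraph has no partial correlation, no covariate-only model to subtract, and no test of the gene's coefficient. The 1-5% false discovery rate belongs to the preceding step, the pre/post comparison of expression.

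Other sections bear on selection. Specific Aim 1c in Section D.2.e describes a correlation analysis to find the 100 genes and says that statistical strength and likely function will both count. The end of the microarray statistics in D.2.f adds pathway analysis and Q-RT-PCR validation. No section says how these combine with the score.

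**The concern.** The adjusted R-squared of a model holding a gene and several covariates answers how well all of them together predict the response. The plan reads it as the strength of the link between the gene and the trait. If age, sex, BMI or a baseline value predicts the response at all, every gene is credited with that prediction, including genes with no effect.

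Two things are at stake. A reported gene-trait association could consist largely or wholly of covariate signal, and a high value on one trait beside a low value on another could say nothing about the gene. Also, a score that adds these values over traits carries a trait-specific scale factor that nobody chose.

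**Working it through.** **Inputs.** The sample size is 75: "Seventy-five subjects will be recruited for this study" (D.2.a). The covariates for the per-gene models are not listed. Four are assumed, giving k = 5 regressors with the gene. Covariate R-squared is not given anywhere, so a range is assumed.

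**The plan's own figure.** None is stated for this score. The nearest is in D.2.e: 80% power for a correlation of 0.31 with 75 subjects. At an assumed two-sided 5% level, a noncentral t calculation gives 79.6% and Fisher's z 77.6%. That figure is not disputed and serves only as a yardstick: a gene alone with sample r = 0.31 has adjusted R² = 1 − (1 − 0.0961) × 74/73 = 0.084.

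**Step 1: a gene with no effect.** Let R²c be the covariate R² and p the gene's partial correlation. Then

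1 − R² = (1 − R²c)(1 − p²), and adjusted R² = 1 − (74/69)(1 − R²c)(1 − p²).

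For a null gene the mean of p² is 1/70, so 1 − p² averages 69/70. The mean adjusted R² is then 1 − (74/69)(69/70)(1 − R²c) = 1 − (74/70)(1 − R²c). This is exactly the adjusted R² of the covariates alone (75 − 4 − 1 = 70). The correction cancels the gene's chance contribution and leaves the covariates' share in place.

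Simulation (n = 75, four covariates, 3,000 runs per row) agrees:

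| Covariate R² (assumed) | Null gene, mean adjusted R² | 5-95% range | Runs above 0.084 |
|---|---|---|---|
| 0 | 0.00 | −0.06 to 0.08 | 5% |
| 0.10 | 0.10 | −0.01 to 0.24 | 53% |
| 0.20 | 0.20 | 0.06 to 0.35 | 90% |
| 0.30 | 0.29 | 0.14 to 0.45 | 99% |

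At 0.25 the mean is 0.24 to 0.25. Six covariates give nearly the same values.

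**Step 2: what covariate R² is plausible.** D.2.e defines response as change divided by the pre-treatment value. If baseline is among the covariates, the response is regressed on its own denominator. With an assumed coefficient of variation of 0.3 to 0.5 and a pre/post correlation of 0.5 to 0.85, baseline alone gives R² of about 0.07 to 0.23.

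**Step 3: order within a trait.** With the same subjects and covariates, R²c is common to all genes, so adjusted R² rises with p² alone. The simulated rank correlation between adjusted R² and |p| was 1.0. If subject sets differ, the common part no longer cancels exactly: with 68 of 75 usable in each tissue (assumed) and covariate R² 0.3, the between-tissue shift had an SD of 0.04.

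**Step 4: the multi-trait score.** With fixed weights w for each trait,

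score = [sum of w(1 − (74/69)(1 − R²c))] + (74/69) × [sum of w(1 − R²c)p²].

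The first bracket is the same for every gene, so genes are ordered by the sum of w(1 − R²c)p². A partial correlation of 0.31 (p² = 0.096) contributes 0.096 at R²c = 0, 0.086 at 0.1, 0.077 at 0.2 and 0.067 at 0.3. Over the Step 2 range the factor runs from 1 − 0.07 = 0.93 to 1 − 0.23 = 0.77, a ratio of 0.77/0.93 = 0.83 between the extremes.

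**Step 5: the weights.** Four simulated traits had covariate R² of 0.5, 0.3, 0.1 and 0. Average absolute first-component weights were:

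| Decomposition | 0.5 | 0.3 | 0.1 | 0 |
|---|---|---|---|---|
| Adjusted R² matrix, uncentred | 0.54 | 0.32 | 0.11 | 0.03 |
| Adjusted R² matrix, centred covariance | 0.01 | 0.04 | 0.22 | 0.74 |
| Adjusted R² matrix, correlation | 0.25 | 0.26 | 0.25 | 0.24 |
| Trait responses | 0.25 | 0.25 | 0.25 | 0.25 |

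The first two follow covariate R² in opposite directions. The last two do not follow it.

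**The case against.** The strongest reply is that this is an exploratory ranking step in permissive language (the coefficient *can be* used), and that ranking within a trait is untouched. This stands. A reader might infer that null genes would overtake real ones for insulin sensitivity, but Step 3 shows that they would not. Setting a real gene on one trait against a null gene on another is also a comparison the score never makes, because every gene is summed over the same traits.

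Three further inferences go beyond the documents:

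- **That the primary trait would count least.** This needs both its covariate R² and the weights, and neither is given.
- **That the score decides the 100 genes.** Correlation analysis, likely function, pathways and Q-RT-PCR also enter.
- **That baseline must be in these models.** The sentence "All analyses will also be adjusted for the baseline (pre-TZD treatment) value" closes the Aim 1a paragraph. The per-gene models serve Aim 1c, and their covariates are not listed.

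Large covariate R² values lack support too. Section D.2.a reports, from limited preliminary data, that initial insulin sensitivity does not seem to affect the ability to improve. Section B.2 says that predictors of response are not yet known. If covariates explain nothing, the error vanishes.

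Finally, subtracting the covariate-only adjusted R² would also bring a null gene to zero on average. Preferring the partial correlation is a choice of scale. The reason for it is that the subtracted version keeps the factor (1 − R²c), so traits would still not share a scale.

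None of this makes the whole-model coefficient a measure of the gene's association.

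**Conclusion.** The association measure is wrong as written. It credits each gene with whatever the covariates explain: about 0.10 for a null gene at covariate R² of 10%, and 0.24 to 0.25 at 25%. These are assumed values, since the documents give none. The reported values therefore cannot be read as gene effects or compared between traits.

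The effect on the multi-trait score is real but limited in what can be claimed. With fixed weights, gene effects are scaled by (1 − covariate R²). With unspecified principal-component weights, the net direction is open. A reader might infer that the published associations would mostly describe baseline and demographics; that would need covariate R² well above anything the documents support.

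**What to change.** In the Statistical approach paragraph of D.2.f:

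1. Replace the model's adjusted R-squared with the gene's partial correlation with the trait response given the covariates. Report its sign and p-value, and use its square in the score. It comes from the fitted model already planned: p = t/√(t² + residual df), where t is the gene coefficient's t statistic (69 residual df with five regressors). A partial correlation of 0.31 then contributes 0.096 whatever the covariates explain, and a null gene averages 1/70 = 0.014 on every trait with that many regressors.
2. List the covariates, say whether the baseline value is among them, and use the same set for every gene within a trait.
3. Compute any principal-component weights from the trait responses, not from a matrix of R-squared values, and state the centring, scaling and component.

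The cost is wording only: no new data, no extra models and no change in sample size.

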Pharmacogenomics of Thiazolidinediones

NCT01135394

2006-11-27

RESEARCH PLAN

A. SPECIFIC AIMS

The Thiazolidinediones (TZDs) are a class of insulin sensitizing drugs used in the treatment of type 2 diabetes (T2DM). In addition, trials suggest that the TZDs may be useful in the prevention of progression from impaired glucose tolerance to T2DM and have salutary effects on other aspects of the metabolic syndrome. However, clinical and mechanistic studies indicate that not all patients exhibit the expected response to TZDs. Approximately 1/3 of those treated show little or no improvement in insulin sensitivity or HbA1c.

The TZDs are ligands for the nuclear receptor peroxisome proliferator activated receptor-gamma (PPAR γ). When this receptor is activated by TZDs, many genes involved in adipogenesis and insulin signaling are up- or down-regulated.

The overall objective of this proposal is to define the molecular and genetic basis of TZD responsiveness using a phenotype to genotype approach and state-of-the-art functional genomics and high-throughput genetics. Our ***hypotheses*** are:

- (1) Differences in clinical response (primarily improvement in insulin sensitivity) can be defined at the molecular level as differences in expression of genes involved in TZD-activated pathways.
- (2) Genes whose expression change is correlated to clinical response can be identified through cDNA microarrays of muscle and fat, the two target tissues for TZDs.
- (3) Sequence variants in these candidate genes will determine TZD response, particularly sequence variants within regulatory regions.

To directly test these hypotheses, the ***Specific Aims*** of this proposal are to:

1. Perform comprehensive testing in 75 individuals before and after a 3-month rosiglitazone intervention and characterize the variability in TZD response at the physiological, cellular, and molecular levels. The primary TZD response trait will be changes in insulin sensitivity as measured by an intravenous glucose tolerance test (IVGTT). We will also define secondary response traits, which will include body fat composition and distribution (DXA and abdominal CT), serum lipid levels (HDL, LDL, triglycerides, lipoprotein particle sizes), inflammatory markers (hsCRP, SAA, IL1 β , IL6, TNF α), prothrombotic factors (plasminogen activator inhibitor 1; PAI-1), adipokines (leptin, adiponectin), and adipocyte metabolism (glucose uptake, lipolysis). From these data, we will:

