[figure not shown]

Figure 7. Haplotype structure of omentins 1 and 2 as imaged by Haplovview.

D. RESEARCH DESIGN AND METHODS

1. Study Overview and Rationale

The overall objective of this proposal is to define the molecular and genetic basis of the inter-individual variation in response to TZDs. We will test the hypothesis that inter-individual variability in TZD response is due, in part, to genetic influences, more specifically sequence variants in one or more candidate genes. The general approach we will use is a phenotype to genotype approach. We will not only be looking at phenotypes on the whole-body level, but also obtain muscle and fat tissue samples to study more immediate phenotypes all the way down to the gene expression level. Because TZDs act by binding to the nuclear receptor PPAR γ to elicit direct and indirect changes in gene expression that ultimately exert their phenotypic effects, we reason that a phenotype to molecular (gene expression) profile to genotype approach would have the highest likelihood of identifying the responsible genes and their variants.

[figure not shown]

Fig. 8. Schematic of overall study design

The proposed study will expand upon an ongoing study of the pharmacogenomics of PPAR γ in which sophisticated phenotyping and microarray studies of fat and muscle are already well underway (see Preliminary Studies). A schematic of the study design and timeline are shown in Figures 8 and 9. We will define the genes whose regulation correlates to TZD response. Comparisons of gene expression profiles of the same tissue in the same person pre- and post- intervention should minimize many of the problems associated with most microarray experimental designs and should minimize the number of false positive (and false negative) results.

Furthermore, we will confirm these differences by real-time PCR on RNA from the same sample in which the microarray studies were performed. Confirmed genes whose up- or down-regulation is

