Unsupervised clustering techniques will also be used to cluster the subjects according to the similarity of their gene expression profiles (before and after treatment), independently of clinical diagnosis or other investigator-designated categories. To limit noise and increase the strength of our findings, only genes with ample variability are used for cluster analysis (criterion values for variability will be determined empirically). The Hierarchical Ordered Partition and Collapsing Hybrid (HOPAH) (27) algorithm for building a hierarchical tree of clusters will be used for our cluster analysis. The number of clusters will be determined by Median Split Silhouette (MSS) (62) and biological consideration. The non-parametric bootstrap technique will be used for validating the HOPAH clusters. The clustering analyses will be assessed by using HOPAH package software in Bioconductor (27). Clustering of the

subjects based on gene expression would suggest a distinct, common underlying biological basis for disease in these subjects. Such an outcome could be a significant start in achieving one of our goals – a biology-based, rather than a clinical outcome-based classification of TZD response. Comparison of subject symptoms and clinical outcomes within- and across subject clusters based defined by gene expression profiling could be indicative of differences among subjects in response of TZD treatment.

Because the regulation of gene expression is a dynamic process, it is also important to identify and characterize changes in gene expression in response of TZD treatment among subject subgroups defined by expression profiling. Storey, et al. (73) proposed a general statistical method that identifies genes differentially expressed over time among different classes and have developed freely available software called EDGE. It is applicable to detecting differences in the behavior of expression in response to TZD treatment among different subgroups of the subjects. In addition to the pre-post comparison for each subgroup described above, the EDGE program will be used to identify genes that show significant differential expression in response to TZD treatment among different subjects.

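### The clustering meant to classify TZD response appears to use expression levels; clustering on within-person change would match the goal better and avoid clusters that may reflect stable differences such as sex

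*Combined protocol and SAP*

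**What the plan says.** Statistical approach (section D.2.f) adds an unsupervised step to the gene-by-gene analyses. It will "cluster the subjects according to the similarity of their gene expression profiles (before and after treatment"), and do so "independently of clinical diagnosis or other investigator-designated categories". As a filter, "only genes with ample variability are used for cluster analysis", with the cut-off to be found empirically. A hierarchical algorithm (HOPACH) is planned. "The number of clusters will be determined by Median Split Silhouette (MSS) (62) and biological consideration", and a bootstrap is used to validate the result. The stated aim is "a biology-based, rather than a clinical outcome-based classification of TZD response". Clinical outcomes are then compared within and across clusters, and EDGE and pre-post comparisons look at treatment-related expression change among the subgroups already formed.

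The rationale in section D.1 rests on pairing: "Comparisons of gene expression profiles of the same tissue in the same person pre- and post- intervention should minimize many of the problems". The enrolment table in section E.6 plans 37 women and 38 men.

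**The concern.** The clusters are meant to describe response, and section D.2.e defines response as a within-person change. The profile at one visit also carries everything that differs stably between people. Sex is the obvious example in a sample split almost evenly; ancestry is a lesser one, because Aim 1 enrols one racial group. Such differences appear in both the before and the after profile, and a variability filter applied to levels would favour the genes that carry them.

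The planned checks would not correct this. The bootstrap tests whether clusters are stable, and a split by sex would be stable. The outcome comparison could show that clusters do not track response, but it could not recover response groups that the clustering had missed. EDGE takes the subgroups as given, so with sex-like clusters it would become a search for genes whose treatment change differs by sex. Genes from these analyses feed the pathway work that helps choose the 100 candidate genes for Aim 2.

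**Working it through.** **Which input does the text describe?** The clustering sentence does not say whether the two profiles are joined, clustered separately or differenced. Three features favour levels:

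1. Statistical approach uses the term expression profile for tissue at one time point, when it contrasts pretreatment with post-treatment subjects.
2. Where change is meant, the plan says so: in the Aim 1c correlations (D.2.e) and in the regressions on differentially expressed genes (D.2.f).
3. Treatment-related change enters this part of the plan only after the subgroups exist, which would be largely redundant if change had already defined them.

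**How much of the distance between two subjects reflects treatment change?** The plan gives no figure to reproduce. Let s² be the stable between-person variance per gene, c² the variance of the treatment change, and e² the noise variance per array, all independent. For joined before and after profiles, the expected squared distance per gene is 2(s² + e²) + 2(s² + c² + e²) = 4s² + 4e² + 2c². Hence:

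- joined levels, share from change: c² / (2s² + 2e² + c²)
- joined levels, share from stable differences: 2s² / (2s² + 2e² + c²)
- change scores, share from change: c² / (c² + 2e²), because s² cancels

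With e² = 0.25 throughout (all values assumed):

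| s² | c² | Levels: stable share | Levels: change share | Change scores: change share |
|---|---|---|---|---|
| 1 | 1 | 2/3.5 = 0.57 | 1/3.5 = 0.29 | 1/1.5 = 0.67 |
| 1 | 0.1 | 2/2.6 = 0.77 | 0.1/2.6 = 0.04 | 0.1/0.6 = 0.17 |
| 2 | 0.25 | 4/4.75 = 0.84 | 0.25/4.75 = 0.05 | 0.25/0.75 = 0.33 |
| 0.25 | 1 | 0.5/2 = 0.25 | 1/2 = 0.50 | 1/1.5 = 0.67 |
| 0.1 | 1 | 0.2/1.7 = 0.12 | 1/1.7 = 0.59 | 1/1.5 = 0.67 |

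The two denominators differ by 2s², so the change share is higher on change scores whenever s² > 0. Whether stable differences dominate the levels depends on s² against c².

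**Does this alter the clusters?** Simulation of 75 subjects (37 and 38 by sex), two thirds responding independently of sex. There were 1,000 genes, of which the 300 most variable were kept. Between-person SD was 0.6 and within-person SD 0.3 (log2); 100 genes responded. Two-means clustering stands in for the planned algorithm. Entries are the percentage of subjects matched under the better labelling; about 54–55% is chance.

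| Sex-linked genes (shift, log2) | Response shift (log2) | Levels: sex | Levels: response | Change: response |
|---|---|---|---|---|
| 50 (1.5) | 0.6 | 100 | 54–55 | 100 |
| 20 (1.5) | 0.6 | 100 | 54–56 | 100 |
| 10 (1.5) | 0.6 | 99–100 | 54–56 | 100 |
| none | 0.6 | chance | 69–70 | 100 |
| 10 (1.5) | 1.0 | chance | 100 | 100 |
| 20 (1.5) | 1.5 | chance | 100 | 100 |

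A second simulation (3,000 genes, top 500, s² = 0.5, e² = 0.25) was scored by the adjusted Rand index, where 1 is perfect agreement and 0 is chance. In ten settings, joined levels followed sex in six (1.0 for sex, 0.0 for response), followed response in three (1.0), and recovered response partly in one (0.28, with no sex-linked genes). Change scores gave 1.0 for response and 0.0 for sex in all ten.

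**The case against.** The strongest reply is that the text leaves the input open, that joined profiles contain the change, and that the size of any problem rests on assumed numbers. Much of this stands. A reader might infer that level-based clusters will mainly reproduce sex and cannot classify response. The documents do not support that: they give no variance components, and strong response signals were fully recovered from levels in several settings. The unfavourable rows use a response shift of 0.6 log2, about 1.5-fold (2^0.6 = 1.52), which is the plan's own example threshold for differential expression. The 1.5 log2 sex shift is about 2.8-fold, and nothing in the plan fixes how many such genes there are.

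Forcing two clusters is also not the planned method. With four clusters on joined levels and 50 sex-linked genes, clusters were 92–97% pure for response at a 1.0 log2 shift, but only 71–72% at 0.6, against a base rate of 50/75 = 67%. A response split can therefore sit below a sex split, depending on effect size.

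A reader might also infer that sex clusters would be reported as response subtypes and that true response signals would stay hidden. The plan is more cautious: it calls clustering a possible start and compares outcomes across clusters. The change-based correlations and regressions stand apart from it. What the reply does not remove is the mismatch between the most natural reading of the input and the purpose given for it.

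**Conclusion.** The point holds as a mismatch between input and purpose, with a possible rather than certain consequence. Read naturally, the clustering uses levels and an unspecified variability filter, yet is offered as a start on classifying response. Depending on unstated variances, the clusters may reflect stable differences such as sex and dilute or miss response groups. In the share calculation, 0.04 to 0.59 of the distance on levels came from treatment change, against 0.17 to 0.67 on change scores. In the simulations, change scores always recovered the response groups and levels did so only in some settings. These results rest on assumed variances, assumed effect sizes and a stand-in algorithm; noisier arrays would make recovery from change less complete than shown. The analysis is secondary and exploratory, so the primary response trait, its analysis and the sample of 75 are untouched. It is a cheap improvement worth making.

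**What to change.** In Statistical approach (D.2.f):

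- For the response classification, state that subjects are clustered on post-minus-pre log expression, separately for muscle and fat.
- Select genes by the variance of that change, not of the level.
- Cross-tabulate the clusters against sex, age and BMI before calling them response classes.
- Report any clustering on baseline levels separately, as a baseline descriptor.

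Do not remove the mean sex difference from the change scores. Differencing already cancels stable sex differences, and removing more could erase a real sex difference in response. The rosiglitazone section (E.1.c, special populations) reports a slightly greater response in women, and section E.6 says that hypotheses about sex will be addressed.

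The cost is a few sentences and a different input matrix, with the same arrays and software. The downside is small: a difference carries noise variance 2e² where a single level carries e².
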